Participants who screened into the study were directed to an online assent (14-17) or consent (18-19) form that explained the study expectations along with risks and benefits. The IRB approved a waiver of parental consent for participants ages 14-17). Participants were asked to provide their consent if interested in taking part by clicking “yes” on the consent form and providing basic contact information (mobile number for texting and email as well as a question on which was their preferred method of contact). Those who provided affirmative consent went through a further confirmation protocol to reduce the risk for bots, scams, or those out of the country to enroll. The protocol included review of metrics from Qualtrics’ internal fraud detection system, ReCAPTCHA and Scamalytics. All prospective participants whose application was flagged as follow were rejected:

Indicator	Reject if
RelevantIDDuplicate	True/1
RelevantIDDuplicateScore	>75
RecaptchaScore	<.5
RelevantIDFraudScore	>30
BallotBoxStuffing	True/1

Young people also were given a chance to indicate they needed more information before making a study decision. Those who marked that option were asked to provide contact information so a study ambassador could follow-up to address any unanswered questions. Once participants’ eligibility, consent, and geographic location (US) were confirmed, participants received a link to the baseline survey.

e. Random assignment process

The 2-arm randomized controlled trial involves randomizing individual participants using an equal allocation (allocation ratio 1:1) to receive the 3T app or access to the attention control website. Participants were randomized after completing their baseline surveys using the randomizer feature of Qualtrics.

f. **Baseline and follow-up data collection**

The primary source of data for the outcome analyses is the self-report survey. The survey was administered two times: Baseline and 3-months post-baseline. The original study design included a 6-month follow-up timepoint that had to be dropped because of delays and challenges in getting the study launched during COVID.

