Outcome name	Description of the outcome, including how it is operationalized (e.g. "The outcome is a yes/no response taken directly from the survey" or "the risk outcome is calculated as the average of the five risk indicator variables").	Source of the measure (e.g. performance measure)	Timing of measure (e.g., 6 months after program ends)
i. Number of times participants reported having been tested for HIV in the last 3 months ^a	Count of number of times reported being tested for HIV in the last 3 months. Constructed from T1_Q55/T3_Q55 (how many times tested for HIV in last 3 months).	Outcome survey	3 months post baseline
ii. Number of times participants reported having been tested for STIs (excluding HIV) in the last 3 months ^a	Count of number of times reported being tested for STIs other than HIV in the last 3 months. Constructed from T3_Q58 (how many times tested for an STI/STDs in last 3 months).	Outcome survey	3 months post baseline
iii. Sexual Communication Self-Efficacy scale	Average of 20 items on a 4-point scale (1 to 4), with a range of 4 - 80, with a higher score indicating better outcomes. Calculate the average if at least 50% of items were answered (10 of 20). Items embedded in and drawn from questions Q46, Q94, Q47, Q48 and Q49.	Outcome survey	3 months post baseline
iv. Condom Attitudes Scale for Adolescents	Average of 21 items on a 4-point scale (1 to 4) with a range from 21 to 84 with higher scores indicating better outcomes. (Two items were omitted from the original 23-item scale.) Ten questions are reverse coded. Items embedded in and drawn from questions Q40 and Q93.	Outcome measure	3 months post baseline
v. Condom use self-efficacy	Average of 4 items adapted from the Sexual Risk Behavior Beliefs and Self-Efficacy Scale scored on a 4-point scale (1 to 4) with a range from 4 to 16 with higher scores indicating better outcomes. Items embedded in and drawn from question Q42.	Outcome measure	3 months post baseline
i. Attitudes towards lube	Average of 3 items on openness to using sexual lubricant on a scale from 1 to 4 with higher scores indicating more positive views towards		

3T Protocol+Impact Analysis Plan		
Version: 2.0		Last updated: 3.8.23

lube (better outcome). The third item is reverse coded. Items embedded in and drawn from question Q41.

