^a If an outcome assessing the number of times has a very skewed distribution, it may be collapsed into a dichotomous variable (e.g, 0 times, 1 or more times) based on the final distribution.

a. Analytic sample

We will use complete case analysis as the benchmark sample for this study. The analytic samples for both primary and secondary outcomes will include all individuals who respond to the questions making up the outcomes at baseline and follow-up and have complete data on the covariates included in each model.

b. Data cleaning

Missing data. We will examine missingness of potential covariates and use data from the follow-up survey to fill in missing values from baseline on covariates that are hypothesized not to change between the two survey timepoints. The primary and secondary outcomes will be analyzed using complete cases.

Inconsistencies. Because of forced skip patterns pre-programmed into the electronic data collection devices, we expect the sexual behavior outcome data to be relatively clean within time points. *Within time* consistencies will be checked on questions asking about the type of sex had in the last 3 months and the number of times respondents had the type of sex across all partners. For respondents with inconsistencies, we will assess patterns across all variables and discuss decision rules. *Across time* inconsistency will be checked on questions asking whether respondents have ever had vaginal or anal sex. With only two data points, we will analyze the data with and without inconsistent cases.

Extreme values. For questions asking about the number of times a behavior occurred we will examine extreme values in the context of other responses and apply a consistent decision rule.

c. Assessment of baseline equivalence

In addition to the baseline measures of the outcomes, we also will assess equivalence of the intervention and control groups at baseline on age and having a main partner. To assess equivalence between groups on each of these variables, we used regression analyses with the variable of interest as the dependent variable and the intervention indicator as the independent variable. The groups are considered not equivalent on a given variable if the *p*-value for the intervention indicator's regression coefficient is < 0.05 using the Wald test.

d. Condition crossover and contamination

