An intent to treat model will be used in the analysis so that participants will be analyzed as randomized to treatment or control and followed up regardless of whether they interact with participants in the other condition.

3T Protocol+Impact Analysis Plan		
Version: 2.0		Last updated: 3.8.23

e. **Analytic approach for primary research questions**

i. **Model specification:**

SPSS will be used to conduct the descriptive and bivariate analyses as well as the multivariable analyses. Statistical significance levels will be set at $p < .05$ unless otherwise noted.

Separate data analyses will be performed on each outcome variable named above and will progress through the following stages:

First, *descriptive analyses* will be used to explore the data on all model variables at baseline and follow up for distributional assumptions and unanticipated patterns that might affect subsequent analyses. For example, as noted in the outcomes table, some outcomes may need to be dichotomized if the distribution is too skewed towards 0.

Second, *bivariate analyses* will be used (1) to compare the baseline demographic and background characteristics of the intervention and control groups and (2) to test for relationships between the outcome variable and potential covariates (confounders) being measures. A potential covariate will be included in the model if: (1) the variable is associated with the condition indicator at $p < 0.15$; and (2) the variable is associated with the outcome at $p < 0.15$ in ***individual bivariate analyses***. Our plan for covariate screening is derived from those suggested in Altman (1991) and Hosmer and Lemeshow (1989). In the latter, it is suggested that $p < .25$ as a screening criterion may be more appropriate than $p < .05$ because the latter often fails to identify variables that may be important to control. We have traditionally “split the difference” and selected a $p < .15$ to preserve degrees of freedom of the model. We routinely include the baseline value of the outcome regardless of screening criteria (Pocock et al, 2002). Below, we clarify which covariates will be included regardless of these screening criteria. (4) Bivariate analyses will also be conducted to assess baseline equivalence for the final primary analytic samples.

Third, *multivariable analyses* will be conducted using regression analyses (linear or logistic) to evaluate the research questions as definitively as possible.

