Each model will include an indicator variable denoting (1) intervention group, (2) the baseline outcome variable, (3) the number of days between the baseline and follow-up survey (if there is a large range), (4) age at baseline, and (5) a set of *a priori* demographics and outcome-related covariates that screened positively as candidates for inclusion in the bivariate screening step.

Covariates

Covariates to be forced into all models on an *a priori* basis:

1. Baseline value of outcome
2. Actual # of days between baseline and follow-up

3T Protocol+Impact Analysis Plan		
Version: 2.0		Last updated: 3.8.23

3. Age at baseline

Race was not included as it was a study eligibility requirement (black identifying).

A priori covariates to be screened into the models:

1. With whom have had sex (cis men only vs cis men+others)
2. Effect of COVID pandemic on their ability to see a romantic or sexual partner (0=not at all, 1=somewhat, 2=very).
3. Effect of COVID pandemic on ability to get condoms (0=not harder, 1=may or may not be harder, 3=harder).
4. Has a main partner.

NOTE: if there is high correlation ($r > .5$) between some of these indicators we will not include them all.

ii. Sample attrition

Attrition analyses will be conducted to examine the rate of attrition by condition. Results from the attrition analyses will help evaluate the need to temper interpretations of outcome results.

iii. Sensitivity analyses

- (1) Sensitivity analyses will be conducted examining the sub-group of participants with matching self-reported birthdates at baseline and the 3-month follow-up and within the allowable age range (14-20).

f. Analytic approach for secondary research questions

Analyses for secondary research questions will proceed using the same steps as described for the primary research questions.

4) Additional planned analyses

Additional exploratory analyses of the impact evaluation data may include the following.

- a. Subgroup analyses based on participants in each condition who used their respective interventions (use evident from log in data vs no use evident) may be completed for the primary and secondary outcome variables.
- b. Analyses of the following variables not specified as primary or secondary:
 - a. Lube Knowledge (which are safe w/latex condoms)
 - b. HIV Knowledge (includes PrEP and PEP awareness)
- c. Examination of impact on primary outcome for those reporting casual partners if sample size warrants this level of exploration.

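### The complete-case rule drops participants with a known 3-month outcome when a baseline item is missing; the cost is a little precision, and it is cheap to avoid

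*Combined protocol and SAP*

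**What the plan says.** Section 3a makes complete case the benchmark. The sample is those who "respond to the questions making up the outcomes at baseline and follow-up and have complete data on the covariates included in each model". Section 3b repeats that primary and secondary outcomes are analysed on complete cases.

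Section 3e.i says: "We routinely include the baseline value of the outcome regardless of screening criteria". The list of covariates forced into all models opens with "Baseline value of outcome", followed by days between surveys and age. Four further covariates enter only if associated with both arm and outcome at p < 0.15.

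The plan already limits the loss in several ways:
- Study Design, section e: "Participants were randomized after completing their baseline surveys using the randomizer feature of Qualtrics". A wholly missing baseline survey is therefore not expected; the issue is unanswered items.
- Table 3 scores participants who report no sex as 0 on the primary count.
- Section 3b will "use data from the follow-up survey to fill in missing values from baseline on covariates that are hypothesized not to change" between surveys. It does not name those covariates, and it does not cover the baseline outcome.
- Table 4, communication scale: "Calculate the average if at least 50% of items were answered (10 of 20"). No such rule is given for the condom attitude, condom self-efficacy or lube scales.

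The only planned sensitivity analysis, on matching birthdates, narrows the sample. No analysis brings back participants lost to a missing baseline value.

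**The concern.** A randomised participant with a known arm and a known 3-month outcome carries information on the treatment effect whether or not he answered every baseline item. Under the rule he is discarded. The forced baseline outcome is the certain route to this. A screened covariate matters only if it enters the model.

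At most 178 participants are available, and the 6-month follow-up was dropped, so known 3-month outcomes are scarce. The plan's own intentions, to analyse as randomised and to score no sex as 0 so that the full sample can be modelled, also favour keeping these participants. What is at stake is precision.

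**Working it through.** The plan states no power calculation, retention rate or item-missingness rate, so there is no figure to reproduce. All rates below are assumptions.

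**Inputs.** From the plan: 178 completed baseline; 1:1 allocation; linear or logistic regression; six act items in the primary count (Table 3); 21 items in the condom attitude scale (Table 4). Assumed: missingness of 2%, 5% or 10% at random; n = 178 (everyone) or 140 at follow-up; baseline to follow-up correlation r of 0.3, 0.5 or 0.7; non-response of 0.25–0.5% per item, independent across items.

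**1. Participants lost.** 178 × 0.02 = 3.6; 178 × 0.05 = 8.9; 178 × 0.10 = 17.8.

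**2. Linear model.** Simulated standard error (SE) relative to no missing data (n = 178, effect 0.4 SD, 5,000 runs per cell):

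| Missing | Complete case | Mean fill + indicator, r = 0.3 | r = 0.5 | r = 0.7 |
|---|---|---|---|---|
| 2% | 1.010 | 1.003 | 1.005 | 1.010 |
| 5% | 1.026–1.027 | 1.005 | 1.010 | 1.023 |
| 10% | 1.054–1.055 | 1.008 | 1.019 | 1.047 |

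At n = 140 and 10% missing, complete case gives 1.055; the fill gives 1.008, 1.020 and 1.049.

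Hand check with missing share m:
- Complete case is about 1/√(1 − m). 1/√0.98 = 1.010; 1/√0.95 = 1.026; 1/√0.90 = 1.054.
- Fill plus indicator is about √(1 + m r²/(1 − r²)), ignoring the extra term. At m = 0.10: √(1 + 0.1 × 0.09/0.91) = 1.005; √(1 + 0.1 × 0.25/0.75) = 1.017; √(1 + 0.1 × 0.49/0.51) = 1.047.

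These agree with the simulation to within about 0.3 percentage points. Mean estimates were 0.396–0.405 against a true 0.40.

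**3. Which rate is plausible for which outcome?** The share without a score if all k items are required is 1 − (1 − q)^k.
- Primary count, k = 6: 1 − 0.9975^6 = 1.5%; 1 − 0.995^6 = 3.0%. That is 178 × 0.015 = 2.7 to 178 × 0.03 = 5.3 people. It supposes that everyone is asked all six act items, which overstates it, since those reporting no sex score 0. The two gate questions are not counted.
- Condom attitudes, k = 21: 1 − 0.9975^21 = 5.1%; 1 − 0.995^21 = 10.0%. This needs every item to be required and missing items to be independent; clustered skipping would lower it.

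**4. Primary count if dichotomised.** Logistic model, arm odds ratio 2.5, 50% prevalence, 2% missing; power with complete case against fill plus indicator:
- n = 178: 81.9 v 82.6 (baseline odds ratio 4); 75.2 v 75.7 (odds ratio 9).
- n = 140: 70.0 v 70.0; 62.8 v 63.6.

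The gain is 0 to 0.8 points. Further runs of this design at 2–3% missing gave 0.2 to 1.0. The simulation error of one such power figure is about √(0.75 × 0.25/5,000) = 0.6 points.

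**5. Item scoring.** With 21 items, 0.5% missing on each and n = 178, the relative SE is:
- r = 0.7: complete case 1.055; mean fill plus indicator 1.049; average of answered items 1.000.
- r = 0.3: 1.055, 1.008 and 1.000.

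Using the answered items is clearly better than replacing a score that has 20 of 21 answers.

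**6. Screened covariates.** With independent tests in a randomised trial, one covariate enters with probability 0.15 × 0.15 = 2.25% (unrelated to outcome) to 15% (always passing the outcome screen). At least one of four enters with probability 1 − 0.9775^4 = 8.7% to 1 − 0.85^4 = 47.8%.

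**The case against.** Complete case with baseline adjustment is a defensible choice, stated clearly and without contradiction. All 178 completed baseline before randomisation, age is an eligibility item, and days between surveys is known for anyone followed up. Missingness may be close to nil. All of this stands, and it limits the point to a minor improvement.

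Timing also counts. The last advertisements ran in July 2022, follow-up was at about 3 months, version 2.0 is dated 3.8.23, and Table 3 speaks of the baseline and follow-up variables as already used. Outcome data may well have been in hand, although the plan does not say so. Replacing the benchmark at that stage would cost credibility for a small gain. This stands too and shapes the fix.

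Three stronger readings are tempting, and the documents do not support them:
- *The arm comparison is biased, or intention to treat is broken.* Exclusion on an item answered before randomisation does not itself favour either arm. Those retained are still compared as randomised.
- *The primary outcome loses power at 5–10% missing.* The only route to such rates is the 21-item attitude scale, a secondary outcome, under an all-items rule. Table 4 describes it as "Average of 21 items on a 4-point scale (1 to 4) with a range from 21 to 84". That range is a sum's (21 × 1 to 21 × 4), so scoring with gaps is unclear, but nothing says that one unanswered item voids the score.
- *Participants who have never had sex drop out through the partner covariate.* Its label, "With whom have had sex (cis men only vs cis men+others"), names no level for them, but the plan does not say that they are coded missing, and the covariate must first pass two screens.

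**Conclusion.** The point holds as a small, avoidable loss of precision. The complete-case rule, with the baseline outcome forced in, excludes participants whose 3-month outcome is known, and the fill-in rule does not reach the baseline outcome.

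For the primary count the loss is probably negligible. For a scale outcome it could reach an SE increase of about 5% if 10% lack a baseline score. The mean fill would then recover most of that at weak to moderate correlation and little at 0.7. If no baseline items are missing, nothing changes.

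These sizes rest on assumed random missingness and assumed item rates. The point concerns missing baseline values; it does not address loss to follow-up. It is at the lowest level of importance: worth considering, and no threat to the trial's conclusions.

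**What to change.** 1. Extend the communication scale's half-of-items rule to the other three scales, at baseline and follow-up: at least 11 of 21, 2 of 4 and 2 of 3 items. This uses the answers given. It also protects follow-up scores, which filling baseline values cannot do.
2. Analyse, as assigned, everyone with a 3-month outcome. Replace a baseline outcome or covariate that is still missing with the overall baseline mean, and add a missing indicator. Omit the indicator if the outcome is dichotomised and fewer than about 10 values are missing. At 2% missing, all those with a missing value shared one outcome in 28% (n = 178) to 37% (n = 140) of simulated trials, which makes the indicator unstable. Without it, at 2% and 5% missing (baseline odds ratio 4), type I error was 4.5–5.0% and the log odds ratio stayed within 1% of its value with no missing data.
3. Report the complete-case result alongside. If outcome data were already in hand when the change is made, keep complete case as the stated benchmark, add step 2 as a sensitivity analysis, and label and date the change.

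When finalising the coding, give participants with no sexual partner yet their own level of the partner covariate, so that they are not coded missing.

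Cost: a scoring rule, indicator columns in SPSS and edits to sections 3a and 3b; no new data. The downside is one or two extra model terms and possible instability of a sparse indicator in a logistic model.

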Attention control condition: The control intervention featured a website containing seven health promotion materials in online pamphlet or post formats focusing on mental health (2 pamphlets), nutrition (2 pamphlets), relationships (2 pamphlets) and COVID (1 poster). Young people were asked to select 4 materials to review as part of their participation.

- Mental Health
 - 5 Ways to Stop Stress
 - Suicide Talk, What To Do If You Hear It
- Nutrition
 - Eating Well With No Time & No Money
 - What's a Serving? Choose healthy serving sizes to stay at a healthy weight.
- Relationships
 - Yes Means Yes, What is Affirmative Consent?
 - Relationship Check, Healthy or Un?
- COVID
 - Actions to Protect Yourself and Others

Study Design

a. Sample

The study was open to participants who self-identify as male, Black, African American, or biracial Black/African American; report being ages 14-19 at baseline; self-identify as cisgender male; report sexual attraction to men; and reside in any state in the United States. The age range was expanded to include young people ages 18-19 in May 2022 after facing significant COVID-related challenges in recruiting young people in the 14–17-year age range.

b. Recruitment approaches

The study went through four distinct recruitment phases to accrue the sample (Table 2). Recruitment was impacted severely by the COVID pandemic, requiring multiple pivots in recruitment plans over a two-year period spanning August 2020 to July 2022. After facing COVID-related and other challenges in our proposed recruitment approaches, the study sample was secured through paid advertising on social networking sites.

Table 2. 3T Recruitment Phases

Phase	Dates	Recruitment Focus	Results
Phase 1: CBO recruitment partners	August- November 2020	We engaged selected CBOs to do direct recruitment for the study through their networks and social media, referring interested youth to the 3T recruitment website directly. We had signed MOUs with the following CBOs: AIDS Alabama; the LGBTQ Center, Long Beach; Michigan Organization on Adolescent Health; Nashville Cares; and Triangle Empowerment Center.	We established MOUs with five agencies; agencies were enthusiastic about study but ultimately not successful in engaging youth due to challenges of COVID and its impact on youth engagement with agency services. No youth were recruited during this phase, and we pivoted to general social media strategies.

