Phase 2: Broad social media and micro influencers	May 2021	We worked with Commando, a company specializing in social media study recruitment and ad placement for LGBTQ populations to use social media (Instagram) to promote the study nationally. At the same time, we identified a small number of micro influencers (2) who were paid to promote the study using IRB approved recruitment messages through their social media channels. We also tried TikTok and Snapchat but those platforms would not allow us to promote the study due to their restrictions on promoting studies (Snapchat) and promoting	Over 800 individuals completed the screener over the launch weekend in May 2021. Nearly all appeared to be out of country and age range but were claiming to be in age range and within the US. We closed recruitment and rejected all surveys coming in during this period because the sample was not our desired population. We also stopped general social media recruitment and moved toward a new phase of more targeted recruitment to avoid international and

		sexually related content (Tik Tok). We also planned to use a snowball sampling approach during this phase, which allowed young people to refer up to three others from their networks and receive a stipend if the individual met eligibility criteria.	national scam attacks. Further, we added an online video screening requirement for age and country verification for those who did screen as eligible. Further, we dropped use of social media influencers as their promotion also contributed to scam attacks. Finally, we also dropped snowball sampling to reduce scam attacks and because it was not yielding expected results in a different study. After this phase, we considered and explored other avenues (e.g., schools and school clubs such as GSAs) but COVID continued to impact schools' and agencies' ability to reach youth and engage with us.

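### The sensitivity analysis filters on age 14-20 with no date for calculating age, while eligibility is 14-19 at baseline (minor)

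*Combined protocol and SAP*

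**What the plan says.** Study Design, a. Sample admits people who "report being ages 14-19 at baseline". The same section explains the upper limit: "The age range was expanded to include young people ages 18-19 in May 2022". The consent process (Study Design, d) agrees, since people who screen in are "directed to an online assent (14-17) or consent (18-19) form"; it has no route for anyone aged 20.

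Analysis, e.iii lists one sensitivity analysis. It is restricted to participants with "matching self-reported birthdates at baseline and the 3-month follow-up and within the allowable age range (14-20"). The sentence does not say whether age is taken at baseline, at follow-up or at both, and it does not explain why the upper limit is 20 rather than 19.

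One other comparison with and without certain cases is planned, under Data cleaning: "With only two data points, we will analyze the data with and without inconsistent cases". It concerns contradictory answers on whether the respondent has ever had vaginal or anal sex, not eligibility. The e.iii analysis is therefore the only one that tests whether participants of doubtful age or identity affect the result.

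**The concern.** A check on eligibility should test against the eligibility rule. Here the rule is 14-19 at a stated time and the check is 14-20 at an unstated time. Two analysts could build different samples from the same sentence, and none of the samples that the wording permits is certain to exclude a person who was 20 at enrolment. If the sensitivity result agreed with the main result, it could be reported as showing that participants outside the age range did not drive the finding, although the filter had not been set to remove all of them.

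**Working it through.** **Inputs.** The eligible age at baseline is 14 to 19 completed years (Study Design, a). The filter is 14 to 20 completed years (Analysis, e.iii). On timing, "The survey was administered two times: Baseline and 3-months post-baseline". The interval varies, because the models include "the number of days between the baseline and follow-up survey (if there is a large range"), but no figure is given. I take 91 days as the central value and 60 to 150 days as the range, with birthdays spread evenly over the year. These are assumptions.

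**Notation.** Let *a* be exact age at baseline and *L* the interval in years: 91/365.25 = 0.249; 60/365.25 = 0.164; 150/365.25 = 0.411. Age at follow-up is *a* + *L*. Eligibility means 14 ≤ *a* < 20.

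**Where 14-20 can come from.** For eligible participants, age at follow-up runs from 14.249 to just under 20.249, which is 14 to 20 in completed years. The share of 19-year-olds who turn 20 before follow-up equals *L*: about 25% (16% at 60 days, 41% at 150 days). So 14-20 is the correct span of ages that eligible participants can have at follow-up. It is not the correct span at baseline.

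**Who passes under each reading.**

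| When the range is applied | Baseline ages that pass | Share of those aged 20 at baseline who pass |
|---|---|---|
| Baseline | 14 ≤ *a* < 21 | 100% |
| Follow-up only | 14 − *L* ≤ *a* < 21 − *L*, i.e. 13.751 to 20.751 | 1 − *L* = 75% (84% at 60 days, 59% at 150 days) |
| Both surveys | 14 ≤ *a* < 21 − *L*, i.e. 14 to 20.751 | 75% (same range) |
| 14-19 also required at baseline | 14 ≤ *a* < 20 | 0% |

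The first three rows use only the condition in e.iii. The fourth adds one that e.iii does not contain. The second row also lets through someone aged 13.751 to 14 at enrolment.

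**Check on the obvious alternative.** Changing 20 to 19 and applying it at follow-up would drop the eligible 19-year-olds who have since turned 20, again about 25% of them (16% to 41%). The upper limit alone is not the problem. The date has to be fixed as well.

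**The case against.** The strongest reply is that 14-20 is simply the eligibility rule carried forward. The sentence names the 3-month follow-up, an eligible 19-year-old can be 20 by then, and the authors may have meant the 14-19 baseline rule to stay in force. This is probably how the figure arose. On that reading nobody aged 20 at baseline passes. The reply explains the number but does not supply the missing condition, which the reader has to add.

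A reader might go further and infer that 20-year-olds were enrolled and sit in both analyses. The documents do not support that. Table 2 describes the 178 enrolled as eligible and no age distribution is given, so any count would be a guess. The Phase 2 remark, "Nearly all appeared to be out of country and age range but were claiming to be in age range and within the US", is tempting evidence, but it concerns May 2021, a year before ages 18-19 were added, and all surveys from that period were rejected. Afterwards the team added video screening for age and country. The consent section does not restate that step for Phase 4, and video may not separate 19 from 20, but self-report was not the only documented safeguard. Nor do the documents show that people just over the limit are the likeliest ineligible group.

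The mechanism is also narrow. Someone who gives the same false, in-range birthdate at both surveys passes any age limit. The wording matters only for a person who screened in and then twice reported a birthdate outside the baseline range. Finally, the primary complete-case analysis does not use this filter. All of these limits stand, and they make the point minor.

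**Conclusion.** The point holds as a minor conflict between a stated rule and the eligibility criterion. Wherever the 14-20 condition is applied, it can pass a person who was 20 at enrolment: all such people at baseline, or about 75% at follow-up, given a 91-day interval and evenly spread birthdays. Applied at follow-up alone, it can also pass someone just under 14 at enrolment. These are shares of a group whose size is not given and may be zero. No effect on any estimate is shown. Only the meaning of one sensitivity analysis is at stake.

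**What to change.** In Analysis, e.iii (1), replace the 14-20 range with: *age 14 to 19 at the date of the baseline survey, calculated from the reported birthdate*. This keeps every eligible 19-year-old who turns 20 during follow-up and removes anyone whose reported birthdate puts them outside the eligibility range at either end. Because the analysis already requires the two birthdates to match, there is no question of which one to use.

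The cost is one phrase. Birthdates are reported at both surveys, and the plan already uses the number of days between surveys, so the survey dates are to hand. The sensitivity sample may be slightly smaller. If it has already been built, it can be rebuilt from the same data and the change recorded, as the plan's purpose statement asks for deviations.
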